15. ETHICAL CONSIDERATIONS

15.1 Compliance with Laws and Regulations

Patients who comply with the requirements of the protocol, are tolerating study treatment, and may be receiving benefit will be offered dosing beyond Cycle 1 at the investigator's discretion after a careful assessment and thorough discussion of the potential risks and benefits of continued treatment with the patient. Such patients may have the option to receive abemaciclib or abemaciclib plus MK-6482 treatment as long as they continue to experience clinical benefit in the opinion of the investigator until the earlier of unacceptable toxicity, symptomatic deterioration attributed to disease progression, or any of the other reasons for treatment discontinuation listed in **Section 5.5**.

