5.5 General Concomitant Medication and Supportive Care Guidelines

Concomitant medication is defined any medication, over-the-counter preparation, or alternative therapies used within 7 days prior to the screening evaluation and prior to the last study visit. All concomitant medications administered within 14 days prior to Cycle 1, Day 1 and during the study until last study visit will be collected on study-specific electronic Case-Report Forms (eCRFs). The reason(s) for treatment and dates of treatment should be reported to the investigator and recorded as instructed on the study-specific eCRFs.

The Overall PI should be alerted if the participant is taking any agent known to affect or with the potential to affect selected CYP450 isoenzymes. **Appendix B** presents guidelines for identifying medications/substances that could potentially interact with the study agent(s).

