5.6 Criteria for Taking a Participant Off Protocol Therapy

Duration of therapy will depend on individual response, evidence of disease progression and tolerance. In the absence of treatment delays due to adverse event(s), treatment may continue until one of the following criteria applies:

- Disease progression
- Intercurrent illness that prevents further administration of treatment
- Unacceptable adverse event(s)
- Participant demonstrates an inability or unwillingness to comply with the oral medication regimen and/or documentation requirements

- Participant decides to withdraw from the protocol therapy
- Pregnancy
- General or specific changes in the participant's condition render the participant unacceptable for further treatment in the judgment of the treating investigator

Participants will be removed from the protocol therapy when any of these criteria apply. The reason for removal from protocol therapy, and the date the participant was removed, must be documented in the case report form (CRF). Alternative care options will be discussed with the participant.

When a participant is removed from protocol therapy and/or is off of the study, the participant's status must be updated in OnCore in accordance with REGIST-OP-1.

The overall PI must be notified in case of unusual or life-threatening adverse events.

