8.1.9 Destruction and Return

Drug should be destroyed at the site, after the investigator approves the drug destruction policy at the site. Drug will not be returned to Eli Lilly and Company. Destruction will be documented in the Drug Accountability Record Form.

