15.3 Institutional Review Board or Ethics Committee Approval

This protocol, the informed consent document, and relevant supporting information must be submitted to the IRB for review and must be approved before the study is initiated. The study will be conducted in accordance with FDA, applicable national and local health authorities, and IRB requirements.

The Principal Investigator is responsible for keeping the IRB apprised of the progress of the study and of any changes made to the protocol as deemed appropriate, but in any case, the IRB must be updated at least once a year. The Principal Investigator must also keep the IRB informed of any significant AEs.

Investigators are required to promptly notify their respective IRB of all adverse drug reactions that are both serious and unexpected. This generally refers to SAEs that are not already identified in the Investigator's Brochure and that are considered possibly or probably related to the molecule or study drug(s) by the investigator. Some IRBs may have other specific AE requirements to which investigators are expected to adhere. Investigators must immediately forward to their IRB any written safety report or update provided by Exelixis or Bristol Myers Squibb (e.g., IND safety report, Investigator's Brochure, safety amendments and updates, etc.).

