15.4 Confidentiality

Patient medical information obtained by this study is confidential and may be disclosed to third parties only as permitted by the ICF (or separate authorization to use and disclose personal health

information) signed by the patient or unless permitted or required by law. Medical information may be given to a patient's personal physician or other appropriate medical personnel responsible for the patient's welfare for treatment purposes.

Data generated by this study must be available for inspection upon request by representatives of the FDA and other regulatory agencies, national and local health authorities, Exelixis representatives and collaborators, Bristol Myers Squibb and representatives and collaborators, and the IRB/Ethics Committee (EC) for each study site, if appropriate.

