15.6 Study Medication Accountability

The recipient will acknowledge receipt of the drugs provided by Exelixis and Bristol Myers Squibb, indicating shipment content and condition. Damaged supplies will be replaced.

Accurate records of all study drugs dispensed from and returned to the study site should be recorded by using the institution's drug inventory log or the National Cancer Institute drug accountability log.

All partially used or empty containers should be disposed of at the study site according to institutional standard operating procedure. Return unopened, expired, or unused study drug with the Inventory of Returned Clinical Material form as directed by Genentech.

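### Section 15 conflicts with the rest of the protocol on when treatment ends, whose safety reports are forwarded, which companies may inspect data, and what happens to unused drug

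*Combined protocol and SAP*

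**What the plan says.** On the end of treatment, section 15.1 offers dosing beyond cycle 1 for as long as the investigator judges that the patient benefits, "until the earlier of unacceptable toxicity, symptomatic deterioration attributed to disease progression, or any of the other reasons for treatment discontinuation listed in" Section 5.5. The heading found at that number is "5.5 General Concomitant Medication and Supportive Care Guidelines". The discontinuation reasons stand one section later, under "5.6 Criteria for Taking a Participant Off Protocol Therapy". Disease progression is the first reason listed there, and the rule is mandatory: "Participants will be removed from the protocol therapy when any of these criteria apply". Sections 1.1 and 5.1 both end treatment at radiographic progression, and 5.1 cites 5.6 correctly.

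On the companies, section 15.3 requires investigators to pass to their IRB "any written safety report or update provided by Exelixis or Bristol Myers Squibb". Section 15.4 opens trial data for inspection to, among others, "Exelixis representatives and collaborators, Bristol Myers Squibb and representatives and collaborators". Section 15.6 has drug received from the same two companies and then instructs sites: "Return unopened, expired, or unused study drug with the Inventory of Returned Clinical Material form as directed by Genentech". Sections 8.1.5 and 8.1.7 name Eli Lilly as the supplier of abemaciclib, and 8.2.5 and 8.2.7 name Merck as the supplier of MK-6482. Section 8.1.9 has abemaciclib destroyed at the site and adds: "Drug will not be returned to Eli Lilly and Company". Section 8.2.9 says the same of MK-6482 and Merck.

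**The concern.** These are working instructions to sites. They govern how long a patient is dosed, which safety documents reach an IRB, who may inspect the data, and how drug is disposed of. On each of these, section 15 says something different from the section that owns the subject.

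The treatment-duration clause matters most for the data. Read literally, 15.1 does not name radiographic progression as an end point for dosing, and its cross-reference does not lead to any list that does. If some sites dose past asymptomatic radiographic progression and others stop, several quantities depend on the site's reading:

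- cumulative exposure and adverse-event totals;
- the adverse-event windows that run from the last dose, such as the 90 days for serious events in 7.3.4;
- the date of the progression biopsy;
- possibly overall survival.

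The company names matter because, taken literally, they point the forwarding and inspection clauses at firms that supply neither drug and leave out the two that do.

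**Working it through.** The plan gives no figure on this point and no arithmetic decides it. The check sets the passages side by side.

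**Treatment duration**

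1. Sections 1.1, 5.1 and 5.6 agree that treatment ends at progression. Sections 1.1 and 5.1 specify that it is radiographic; 5.6 makes removal compulsory.
2. Section 15.1 as written gives three ends: unacceptable toxicity, symptomatic deterioration attributed to progression, and the other reasons in Section 5.5. Sections 5.5 to 5.5.3 contain no discontinuation reasons, so the third end is empty. A patient with radiographic progression and no symptoms then meets none of the ends in 15.1, but must come off drug under 5.6.
3. Now read the reference as 5.6. The clause takes the earliest of its ends, and 5.6 includes disease progression, so treatment ends there and most of the conflict disappears.
4. Two sources of ambiguity survive that correction. First, if any progression ends treatment, a separate trigger for progression with symptoms does no work. A site could take the word *other* to mean that 15.1 has already dealt with progression, in its symptomatic form only. The term also has a second meaning: the note under Table 16 in 12.1.4.4 uses it for decline without objective progression. Second, 5.5.3 contemplates radiotherapy, ablation or surgery at progression, says the participant may continue the study, and advises caution when abemaciclib is given alongside radiotherapy. It does not say how this fits with compulsory removal under 5.6.

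**What depends on it**

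5. Best overall response runs only to progression (12.1.4.4). Duration of response ends at the first documented progression or death (12.1.4.5). Progression-free survival ends at the earlier of progression or death (12.1.6 and 14.1.2). Dosing after progression does not enter these definitions.
6. Exposure and adverse events do continue past progression if dosing does. Note 20 to the study calendar places the progression biopsy at least 2 weeks after the last dose, so later stopping means a later biopsy. Sections 1.1 and 9.2.1 limit that biopsy to patients with an initial response. Section 14.3.8 expects tissue at progression from 40% of participants (0.40 × 37 = 14.8, stated as 15).

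**Companies and drug disposal**

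| Subject | Section 15 | Elsewhere |
|---|---|---|
| Supplier | Exelixis and Bristol Myers Squibb (15.6) | Eli Lilly (8.1.5, 8.1.7); Merck (8.2.5, 8.2.7) |
| Source of safety reports to forward to the IRB | Exelixis or Bristol Myers Squibb (15.3) | 7.3.3 and Appendix C 3.9.5 cover part of this without those names |
| Company access to data or records | Exelixis and Bristol Myers Squibb (15.4) | 7.3.3 requires relevant records to be made available to Lilly |
| Unused drug | Returned as Genentech directs (15.6) | Destroyed at the site, not returned (8.1.9, 8.2.9) |

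7. Every row is a mismatch. None can be put down to redaction or PDF conversion, since the names and instructions are legible and complete.

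**The case against.** The best defence is that the stopping-rule conflict is mostly a misnumbered reference. The intended target is plainly 5.6, and 5.1 cites it correctly. Section 15.1 is permissive, while 5.6 is mandatory and agrees with 1.1 and 5.1. A careful site would therefore stop at progression. This largely stands. It does not explain the symptom-based trigger, and it does not deal with 5.5.3.

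Several stronger readings are tempting, and the documents do not support them.

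- *Every patient with asymptomatic radiographic progression faces two opposite rules.* This holds only if the reference is taken literally as 5.5.
- *The primary response rate or progression-free survival is compromised.* Their definitions already close at progression, and overall survival is a descriptive Kaplan-Meier estimate in each arm (14.3.4).
- *Lilly and Merck safety information has no route to IRBs.* Section 15.3 itself carries a company-neutral duty to notify IRBs of serious and unexpected reactions. Section 7.3.3 requires new safety information to be reported to IRBs. Appendix C 3.9.5 covers IND safety reports. Only the forwarding sentence is defective.
- *The data of all 37 participants are exposed to unrelated companies.* Section 15.4 begins by limiting disclosure of patient medical information to what the consent form or the law allows. The consent form is not available here, so actual disclosure is not shown.
- *Section 15 was lifted whole from another trial.* For 15.3, 15.4 and 15.6 this is a reasonable inference from the names. Section 15.1 names abemaciclib and MK-6482, so it was at least adapted.

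**Conclusion.** The point holds as a set of internal contradictions in operative text, with limited consequence for the efficacy results. Section 15.1 has a wrong cross-reference. Even with that corrected, its wording and 5.5.3 leave room for sites to differ on dosing after asymptomatic radiographic progression. The effect falls on exposure, adverse-event data, biopsy timing in initial responders and possibly overall survival. Its size cannot be derived, because the documents do not say how many patients will progress without symptoms or how sites will read the clause. Best response, duration of response and progression-free survival are not directly affected.

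The company names in 15.3, 15.4 and 15.6 are wrong against section 8, and the return instruction in 15.6 contradicts 8.1.9 and 8.2.9. These findings need no assumption beyond section 8 being right about who supplies the drugs, which 7.3.3 and 7.3.4 support by directing serious-event reports to Lilly and Merck. The correction should be made, but it does not threaten the design.

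**What to change.** Reconcile 15.1 with 1.1, 5.1, 5.5.3 and 5.6 so that one stopping rule stands, and correct the reference to Section 5.5. Which rule stands is the sponsor's decision. The reconciled text should settle what the symptom-based trigger in 15.1 means and how local therapy at progression under 5.5.3 relates to removal under 5.6. No new statement on the endpoints is needed.

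Replace the company names in 15.3, 15.4 and 15.6 with Eli Lilly and Merck, and check the result against the disclosure list in the consent form. Reconcile the return instruction in 15.6 with 8.1.9 and 8.2.9.

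The cost is a text correction in the next amendment and one check of the consent form. Sample size, assessments and analyses are unchanged.

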15.2 Informed Consent

The informed consent document must be signed by the subject or the subject's legally authorized representative before his or her participation in the study. The case history for each subject shall document that informed consent was obtained prior to participation in the study. A copy of the informed consent document must be provided to the subject or the subject's legally authorized representative. If applicable, it will be provided in a certified translation of the local language. Signed consent forms must remain in each subject's study file and must be available for verification by study monitors at any time.

15.3 Institutional Review Board or Ethics Committee Approval

This protocol, the informed consent document, and relevant supporting information must be submitted to the IRB for review and must be approved before the study is initiated. The study will be conducted in accordance with FDA, applicable national and local health authorities, and IRB requirements.

The Principal Investigator is responsible for keeping the IRB apprised of the progress of the study and of any changes made to the protocol as deemed appropriate, but in any case, the IRB must be updated at least once a year. The Principal Investigator must also keep the IRB informed of any significant AEs.

Investigators are required to promptly notify their respective IRB of all adverse drug reactions that are both serious and unexpected. This generally refers to SAEs that are not already identified in the Investigator's Brochure and that are considered possibly or probably related to the molecule or study drug(s) by the investigator. Some IRBs may have other specific AE requirements to which investigators are expected to adhere. Investigators must immediately forward to their IRB any written safety report or update provided by Exelixis or Bristol Myers Squibb (e.g., IND safety report, Investigator's Brochure, safety amendments and updates, etc.).

15.4 Confidentiality

Patient medical information obtained by this study is confidential and may be disclosed to third parties only as permitted by the ICF (or separate authorization to use and disclose personal health

information) signed by the patient or unless permitted or required by law. Medical information may be given to a patient's personal physician or other appropriate medical personnel responsible for the patient's welfare for treatment purposes.

Data generated by this study must be available for inspection upon request by representatives of the FDA and other regulatory agencies, national and local health authorities, Exelixis representatives and collaborators, Bristol Myers Squibb and representatives and collaborators, and the IRB/Ethics Committee (EC) for each study site, if appropriate.

15.5 Study Medical Monitoring Requirements

This clinical research study will be monitored both internally by the PI and externally by the IRB. In terms of internal review, the PI will continuously monitor and tabulate AEs. Appropriate reporting to the IRB will be made. The PI of this study will also continuously monitor the conduct, data, and safety of this study to ensure that:

- Interim analyses occur as scheduled,
- Stopping rules for toxicity and/or response are met,
- Risk/benefit ratio is not altered to the detriment of the subjects,
- Appropriate internal monitoring of AEs and outcomes is done,
- Over-accrual does not occur,
- Under-accrual is addressed with appropriate amendments or actions, and
- Data are being appropriately collected in a reasonably timely manner.

Routine monitoring will be carried out via a periodic team conference among investigators during which toxicity data, including all SAEs, will be reviewed and other issues relevant to the study such as interim assessment of accrual, outcome, and compliance with study guidelines, will be discussed. Monitoring will be carried out on an ongoing basis. The severity, relatedness, and whether or not the event is expected will be reviewed.

15.6 Study Medication Accountability

The recipient will acknowledge receipt of the drugs provided by Exelixis and Bristol Myers Squibb, indicating shipment content and condition. Damaged supplies will be replaced.

Accurate records of all study drugs dispensed from and returned to the study site should be recorded by using the institution's drug inventory log or the National Cancer Institute drug accountability log.

All partially used or empty containers should be disposed of at the study site according to institutional standard operating procedure. Return unopened, expired, or unused study drug with the Inventory of Returned Clinical Material form as directed by Genentech.

15.7 Data Collection

The study coordinator and investigators are responsible for ensuring that the eligibility checklist is completed in a legible and timely manner for every patient enrolled in the study, and that data are recorded on the appropriate forms and in a timely manner. Any errors on source data should be lined through, but not obliterated, with the correction inserted, initialed, and dated by the study coordinator or PI. All source documents will be available for inspection by the FDA and the DFCI IRB.

16. PUBLICATION PLAN

The data will be collected by the Principal Investigator and analyzed by the Principal Investigator and the statistical team at DFCI. It is anticipated that the results would be made public within 12 months of reaching the end of the study. The end of the study is the time point at which the last data items are to be reported, or after the outcome data are sufficiently mature for analysis, as defined in the section on Sample Size, Accrual Rate and Study Duration. If a report is planned to be published in a peer-reviewed journal, then that initial release may be an abstract that meets the requirements of the International Committee of Medical Journal Editors.

APPENDIX A PERFORMANCE STATUS CRITERIA

ECOG Performance Status Scale		Karnofsky Performance Scale	
Grade	Descriptions	Percent	Description
0	Normal activity. Fully active, able to carry on all pre-disease performance without restriction.	100	Normal, no complaints, no evidence of disease.
		90	Able to carry on normal activity; minor signs or symptoms of disease.
1	Symptoms, but ambulatory. Restricted in physically strenuous activity, but ambulatory and able to carry out work of a light or sedentary nature (e.g., light housework, office work).	80	Normal activity with effort; some signs or symptoms of disease.
		70	Cares for self, unable to carry on normal activity or to do active work.
2	In bed <50% of the time. Ambulatory and capable of all self-care, but unable to carry out any work activities. Up and about more than 50% of waking hours.	60	Requires occasional assistance, but is able to care for most of his/her needs.
		50	Requires considerable assistance and frequent medical care.
3	In bed >50% of the time. Capable of only limited self-care, confined to bed or chair more than 50% of waking hours.	40	Disabled, requires special care and assistance.
		30	Severely disabled, hospitalization indicated. Death not imminent.
4	100% bedridden. Completely disabled. Cannot carry on any self-care. Totally confined to bed or chair.	20	Very sick, hospitalization indicated. Death not imminent.
		10	Moribund, fatal processes progressing rapidly.
5	Dead.	0	Dead.


Antivirals
 
Boceprevir Cobicistat Conivaptan Danoprevir Dasabuvir Elvitegravir Indinavir Lopinavir Nelfinavir Ombitasvir Paritaprevir Ritonavir Saquinavir Telaprevir Tipranavir
 
Anti-Fungals
 
Itraconazole Ketoconazole Posaconazole Voriconazole
 
Antibiotics
 
Clarithromycin Telithromycin Troleandomycin Conivaptan Diltiazem Verapamil Grapefruit juice/star fruit/Seville oranges Idelalisib Nefazodone
	
Carbamazepine Efavirenz Enzalutamide Erythromycin Mitotane Modafinil Nevirapine Oxcarbazepine Phenytoin Rifampin St. John's Wort

1. INTRODUCTION

The Dana-Farber/Harvard Cancer Center Multi-Center Data and Safety Monitoring Plan (DF/HCC DSMP) outlines the procedures for conducting a DF/HCC Multi-Center research protocol. The DF/HCC DSMP serves as a reference for any sites external to DF/HCC that are participating in a DF/HCC clinical trial.

